#### 6.3.4.5 Visit 2: 4 Week Device Fitting

- Bone Conduction testing: Includes unaided bone conduction threshold testing.
- Device programming: Fitting and programming of the Osia 2 sound processor.
- Sound field thresholds: Includes aided thresholds using the Osia 2 sound processor.

### 6.3.4.6 Visit 3: 3 Months Postoperative

- Device programming: Optional and only as needed.
- Device Use Questionnaire: Completed interview-style
- Sound field thresholds: Includes aided thresholds using the Osia 2 sound processor.
- Speech Perception testing: Includes aided testing using CNC words and BKB-SIN sentences and the Osia 2 sound processor.
- SSQ Parent: Completed interview-style based on everyday listening using the Osia 2 sound processor.

#### 6.3.4.7 Visit 4: 6 Months Postoperative

- Device programming: Optional and only as needed.
- Device Use Questionnaire: Completed interview-style
- Sound field thresholds: Includes aided thresholds using the Osia 2 sound processor.
- Speech Perception testing: Includes aided testing using CNC words and BKB-SIN sentences using the Osia 2 sound processor.
- SSQ Parent: Completed interview-style based on everyday listening using the Osia 2 sound processor.

#### 6.3.4.8 Visit 5: 12 Months Postoperative - End of Study

- Document Subject's study completion.
- Ensure device deficiencies, device exposure, adverse events, concomitant medications, and deviations are reviewed, and end dates recorded where appropriate.

### 6.3.4.9 Collected from Baseline

- Concomitant Medication: Includes all prescription medications, routine over-the counter medications, and any use of steroids. Medications used during surgery, vitamins and herbal or natural remedies are not included. Concomitant medications should be reviewed at each visit.
- Protocol Deviations: Includes approved and unapproved deviations.

### 6.3.4.10 Collected from Surgery

- Adverse Events: Includes initial report and review of ongoing adverse events. Adverse events should be reviewed at each visit.
- Device Exposure
- Device Deficiencies

### 6.4 Equipment Used for Evaluations and Procedures

The clinical investigation includes use of equipment to complete assessments. Equipment including programming software and sound equipment (e.g. speakers) are used to assess speech perception performance. Programming software should be kept current at the direction of the Sponsor. For equipment used in this clinical investigation, records of equipment calibration requirements and the calibration records for equipment used to assess Secondary Endpoint testing must be maintained in site files and copies provided to the Sponsor. As part of the Site Initiation Visit, requirements and records should be provided to the Sponsor and records confirmed to be up to date. Records will be monitored at interim monitoring visits, in accordance with the Sponsor's Monitoring Plan.

Osia Fitting Software (OFS) will be used to fit and program the Osia 2 sound processor according to patient preference. All OFS data will be provided to Sponsor for analysis, which may be done automatically or through manual file sharing.

Speech perception testing using CNC words and BKB-SIN sentences will be assessed using a loudspeaker configuration with the signal from the front, zero Azimuth (SO) at head height and 1-meter distance from the subject. The Sponsor may provide equipment (such as test materials, laptop, software, microphone and speaker) if the clinical site does not possess the necessary tools to facilitate testing.

The use of equipment will be logged and reviewed as per the Sponsor's Monitoring Plan.

### 6.5 Sponsor Role in Conduct of the Clinical Investigation

The Sponsor may support certain activities at the clinical investigation site. Sponsor representatives may be present in the operating room with the surgical team and subject. The representative will not provide medical assistance and will not discuss the trial with the subject.

The Sponsor may pay for third party clinical trial support ("coordinator") at clinical investigation sites should there be resource constraints, which may support subject recruitment, data entry and reporting under the authority of the Principal Investigator. The coordinator will be required to comply with hospital policy and will be trained on the CIP and GCP. The coordinator will not complete any activities on behalf of the Sponsor.

A Sponsor representative will review evidence of subject eligibility before the subject is accepted for implantation.

# 7 BENEFITS AND RISKS OF THE INVESTIGATIONAL MEDICAL DEVICE AND CLINICAL

## INVESTIGATION

# 7.1 Anticipated Clinical Benefits

Most recipients of a bone conduction hearing solution will experience an improved hearing performance and quality of life compared to unaided listening.

Potential benefits associated with participation in this clinical investigation include:

- Helping to find better treatments, therapies and/or diagnostic tests in the area of hearing loss or other associated conditions.
- The opportunity to be given a new intervention that may be better for their condition or that has fewer side effects or limitations than they are currently receiving.
- The opportunity to access the newest innovations in the treatment of their hearing loss type.
- Advice, care, and support from trained clinical staff who understand hearing loss and any associated conditions.
- Closer monitoring of their hearing loss.

## 7.2 Anticipated Adverse Device Effects

Based on the available safety reference information and literature, the potential clinical risks have been documented below.

### 7.2.1 Risks Associated with the Surgery

- General risks associated with surgery including pain, scarring, bleeding and infection.
- General risks associated with anesthesia during the surgery (e.g., risks for the heart, lungs, kidneys, liver, and brain) which, in rare cases, can result in death.

### 7.2.2 Risks Associated with Implantation of the Study Device

- Pain or discomfort
- Skin irritation near the implant, swelling or redness near the magnet site, skin breakdown
- Sense of numbness or stiffness in the area of the surgery
- Failure of the implant to properly anchor to the skull-bone due to a lack of adequate bone quantity/quality, trauma, infection, generalized diseases and surgical complications
- Other medical complications that may require additional medical treatment, such as:
  - Concurrent CSF leakage: a leak of CSF (cerebrospinal fluid) through the hole in the skull

- Subdural injury: blood vessels near the brain may burst
- Subcutaneous hematoma: bruises and contusions on the skin
- Skin-flap infection, irritation or inflammation
- Extrusion of the device caused by a foreign body under the skin
- Revision surgery to remove the study implant in the event of device failure
- Failure of the implant or sound processor could result in the perception of an uncomfortably loud sound sensation, intermittent sound, or no sound.
- The implanted magnet may affect MRI (Magnetic Resonance Imaging) procedures. The magnet may influence the MRI scanner or the ability of the scanner to detect certain changes. Under certain circumstances removal of the magnet may be necessary prior to MRI scanning.

### 7.2.3 Risks Associated with Use of the Study Device

- Impact or injury to the head in the area of the Osia implant could damage the implant and result in its failure. Impact to external components (e.g. sound processor) while being worn could result in damage to the device or injury. Young children who are developing motor skills are at greater risk of receiving an impact to the head from a hard object, e.g. table or chair.
- Small parts and accessories could be hazardous if swallowed and could cause choking if ingested or inhaled
- Parents and caregivers should be advised that unsupervised use of long cables (such as the safety line) may present a risk of strangulation.
- Parents and caregivers should routinely check the device for signs of overheating and for signs of discomfort or skin irritation at the implant site. Subjects should remove the processor immediately if there is any discomfort or pain (i.e., if device becomes hot or sound is uncomfortably loud) and inform their hearing care professional.

## 7.3 Risks Associated with Participation in the Clinical Investigation

In addition to the anticipated surgical and adverse device effects of the Osia 2 System, the following risks may also present when participating in the clinical investigation:

- Exposure to sounds produced in the test battery that could be perceived as too loud
- Testing procedures that may produce anxiety or fatigue
- Discomfort and potential abrasion to the ear canal due to placement of insert earphones
- Discomfort associated with the fitting of the Baha 5 Power on the softband
- Possible interactions with concomitant medications and residual risks for the device are not anticipated in this clinical investigation.

### 7.4 Risk Mitigation

The following will be performed during the clinical investigation to mitigate the risks identified above:

- All clinical investigation sites selected have pediatric surgical bone conduction and Osia 2 system experience. The Osia 2 system being implanted is the same as the commercially cleared device currently indicated for children aged 12 years and older.
- The current surgical guidelines associated with the Osia 2 system will be reviewed during Site Initiation, specifically topics surrounding skin flap thickness and bone integrity.
- In addition, the Sponsor's surgical support may be present during surgeries performed by the investigational site(s) either in person or virtually.
- All reported AEs, ADEs and DDs will be regularly reviewed by the Sponsor's Clinical Review Board for the duration of the study to facilitate early detection and appropriate intervention if events are unanticipated with respect to incidence, severity, or outcome.
- All subject's and their parent or legal guardian will be provided with the Osia System Important Information Booklet which contains important safety warnings and cautions related to the device and its use.

# 7.5 Benefit-to Risk Rationale

The clinical safety (risks) and benefit relevant to the anticipated performance of the Osia 2 system were evaluated in the Osia Clinical Evaluation Report (CER) (D1179760) and it was concluded that the data reviewed provided clinical evidence for the safe and effective use of the OSI200 Implant within the Osia 2 System. Significant improvements in both objective and subjective hearing performance were observed with the device as compared to the unaided condition and resulted in an improved quality of life. The Osia 2 system has been cleared in the United States since November of 2019 for children aged 12 years and older. Cochlear-sponsored clinical investigations and a systematic literature review, coupled with the design verification/validation and post-market surveillance data, established that the benefits of the Osia 2 system outweigh the risks.

# 8 STATISTICAL CONSIDERATIONS

### 8.1 General Considerations

There is one primary endpoint and four secondary endpoints. Formal statistical hypothesis tests are planned for the secondary endpoints.

The overall type I error rate will be maintained via a gatekeeping approach whereby statistical tests will proceed in order until a non-significant test is obtained, at which point, formal testing for the purposes of labelling claims will cease. A detailed summary of statistical analysis is documented in the Statistical Analysis Plan (SAP).

### 8.2 Endpoints

### 8.2.1 Primary Endpoint

The primary endpoint is adverse events and serious adverse events Surgery through Visit 4 (6 Months). Events will be summarized by type, frequency, and severity.

### 8.2.2 Secondary Endpoints

### 8.2.2.1 Secondary endpoint 1 – SSQ Parent

Secondary endpoint 1 – SSQ Parent is defined as the mean difference between preoperative and postoperative performance on the Speech Spatial & Qualities of Hearing Questionnaire (SSQ) – Parent version at 6 months post-surgery.

#### 8.2.2.2 Secondary endpoint 2 – PTA 4

Secondary endpoint 2 is defined as the mean difference in individual subject PTA 500, 1, 2, and 4kHz Baseline to 4 weeks post-surgery.

#### 8.2.2.3 Secondary endpoint 3 – CNC Words

Secondary endpoint 3 is defined as the mean difference between baseline unaided speech perception in quiet and the aided condition using the Osia 2 system at 6 months post-surgery on open-set monosyllabic word recognition (CNC Words) in quiet.

### 8.2.2.4 Secondary endpoint 4 – BKB-SIN

Secondary endpoint 4 is defined as the mean difference between baseline unaided speech perception in noise and the aided condition using the Osia 2 system at 6 months post-surgery on an adaptive speech in noise test BKB SIN.

### 8.2.3 Exploratory Endpoints

There are no exploratory endpoints.

### 8.3 Hypotheses

### 8.3.1 Primary Hypothesis

There is no formal hypothesis test for the primary endpoint.

### 8.3.2 Secondary Hypotheses

#### 8.3.2.1 Secondary Endpoint 1 – SSQ Parent

Secondary endpoint 1 will be assessed with the following hypothesis:

 $H_0: \Delta \leq 0$ 

 $H_a: \Delta > 0$ 

where  $\Delta$  represents the difference between preoperative and postoperative performance on the Speech Spatial & Qualities of Hearing Questionnaire (SSQ) – Parent version at 6 months post-surgery, specifically  $\Delta$  = SSQ6 Months – SSQpreop. This difference is parameterized so that a positive value is indicative of a clinical improvement in the questionnaire.

The hypothesis will be evaluated using a one-sample, one-sided 0.025 alpha level t-test for a mean against the null of zero. The objective will be met if the null hypothesis is successfully rejected.

The endpoint will be presented with descriptive statistics and the corresponding two-sided 95% confidence interval based on the t-distribution.

### 8.3.2.2 Secondary Endpoint 2 – PTA4

The secondary endpoint 2 will be assessed with the following hypothesis:

 $H_0: \Delta \leq 0$ 

 $H_a: \Delta > 0$ 

where  $\Delta$  represents the difference between baseline PTA and 4 weeks-post surgery PTA, specifically  $\Delta = _{PTA4}$ weeks – PTApreop. This difference is parameterized so that a positive value is indicative of a clinical improvement.

The hypothesis will be evaluated using a one-sample, one-sided 0.025 alpha level t-test for a mean against the null of zero. The objective will be met if the null hypothesis is successfully rejected.

The endpoint will be presented with descriptive statistics and the corresponding two-sided 95% confidence interval based on the t-distribution.

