## 5.2 Secondary Objective

- To compare preoperative performance compared to postoperative performance in parental questionnaires using the Osia 2 System.
- To compare preoperative unaided bone conduction thresholds to postoperative unaided bone conduction thresholds.
- To compare unaided preoperative speech perception performance to aided speech perception performance postoperatively using the Osia 2 System.
- To compare unaided preoperative adaptive speech in noise performance to aided adaptive speech in noise performance using the Osia 2 System.

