### 6.2.1 Inclusion Criteria

Subjects must meet all of the inclusion criteria described below to be eligible for this clinical investigation.

1. Subjects aged 5 to 11 years of age with the following audiometric criterion:

A conductive or mixed hearing loss and still can benefit from sound amplification. The pure tone average (PTA) bone conduction (BC) threshold (measured at 0.5, 1, 2, and 3 kHz) should be better than or equal to 55 dB HL.

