### 6.3.2 Performance/Effectiveness

### 6.3.2.1 Description of Audiometric Testing

Preoperatively, unaided audiometric thresholds will also be obtained in sound field using narrowband noise. Postoperatively at Device Fitting Visit 2, unaided bone conduction thresholds will be obtained as described in section 6.3.1.2 in the implanted ear to assess the impact of implantation and aid in the fitting of the sound processor. The contralateral ear will be masked accordingly.

• Unaided Sound Field Thresholds: 500, 1000, 2000 & 4000Hz

Aided audiometric thresholds will be obtained preoperatively and in the postoperative aided condition using narrowband noise in sound field. The contralateral ear will be plugged for all tests.

Aided Sound Field Thresholds: 500, 1000, 2000 & 4000Hz

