#### 5.6.3 Secondary Endpoint 2 – PTA

Secondary endpoint 2 is defined as the mean difference in individual subject PTA 500, 1, 2, and 4kHz Baseline to 4 Weeks post-surgery.

### 5.6.3.1 Primary Analysis of Secondary Endpoint 2

The secondary endpoint 2 will be assessed with the following hypothesis:

 $H_0$ :  $\Delta \leq 0$ 

 $H_a$ :  $\Delta > 0$ 

where  $\Delta$  represents difference between baseline PTA and 4 Weeks-post surgery PTA, specifically  $\Delta$  =  $PTA_{4 \ Weeks}$  –  $PTA_{preop}$ . This difference is parameterized so that a positive value is indicative of a clinical improvement.

The hypothesis will be evaluated using a one-sample, one-sided 0.025 alpha level t-test for a mean against the null of zero. The objective will be met if the null hypothesis is successfully rejected.

The endpoint will be presented with descriptive statistics and the corresponding two-sided 95% confidence interval based on the t-distribution.

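### Secondary endpoint 2 (PTA): the written difference counts worse hearing as improvement, the measure is not named, and if bone conduction is meant, correcting the sign does not give a usable test

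*Protocol*

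**What the plan says.** Protocol 8.2.2.2 defines the endpoint as "the mean difference in individual subject PTA 500, 1, 2, and 4kHz Baseline to 4 weeks post-surgery". SAP 5.6.3 says the same: "Secondary endpoint 2 is defined as the mean difference in individual subject PTA 500, 1, 2, and 4kHz Baseline to 4 Weeks post-surgery". Both give frequencies and time points only.

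In protocol 8.3.2.2, delta "represents the difference between baseline PTA and 4 weeks-post surgery PTA, specifically" PTA at 4 weeks minus PTA preop. The hypotheses are H0: delta ≤ 0 and Ha: delta > 0, tested with a one-sample t-test at one-sided 0.025 against zero, with no margin. The accompanying statement is "This difference is parameterized so that a positive value is indicative of a clinical improvement". SAP 5.6.3.1 repeats the formula, hypotheses and statement.

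The direction of the scale is clear from the eligibility rule in protocol 6.2.1: "bone conduction (BC) threshold (measured at 0.5, 1, 2, and 3 kHz) should be better than or equal to 55 dB HL".

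The second secondary objective (protocol 5.2) is "To compare preoperative unaided bone conduction thresholds to postoperative unaided bone conduction thresholds". Protocol 6.3.2.1 says that at Visit 2 "unaided bone conduction thresholds will be obtained as described in section 6.3.1.2 in the implanted ear to assess the impact of implantation", and also to help with fitting. The same section lists "Unaided Sound Field Thresholds: 500, 1000, 2000 & 4000Hz" and the same four frequencies for aided sound field.

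Protocol 8.1 and SAP 5.6 test the secondary endpoints in sequence and stop formal testing for labelling at the first non-significant result. Neither states that the sequence is the endpoint numbering.

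**The concern.** There are three linked faults.

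- **Sign.** A rise in threshold is a loss of hearing, yet the formula makes a rise positive and the next sentence calls positive an improvement. The wording matches that used for SSQ and CNC, where higher is better, so improvement was probably intended. A programmer following the formula and one following the sentence would still reach opposite conclusions.
- **Measure.** Bone conduction and sound-field thresholds are both obtained before surgery and at Visit 2, so an analyst could compute either.
- **Type of test.** A sound-field comparison of unaided with aided hearing asks whether hearing improves, and superiority suits it. Bone conduction is repeated to see whether implantation affected it. There, no change would be a good result, and a superiority test against zero counts it as a failure.

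What is at stake is the formal testing sequence for labelling claims. In numbered order, a failure at endpoint 2 blocks CNC. BKB-SIN also sits behind it, but would fail anyway when the device works, because its own difference has the same sign fault.

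**Working it through.** **1. The plan's own precision figure.** Inputs from protocol 8.4: n = 50, two-sided 95% interval on the t-distribution. Half-width = t(0.975, 49)/√50 = 2.0096/7.0711 = 0.284 SD. This matches the plan.

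**2. Direction.** Eligibility treats 55 dB HL as an upper limit, so lower is better. A child going from 40 to 30 dB HL improves, but delta = 30 − 40 = −10. The statement that positive means improvement is therefore false for the formula beside it.

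**3. Which measure?**

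| Points to bone conduction | Points to sound field |
|---|---|
| Objective 2 names unaided bone conduction; objectives and endpoints are listed in the same order | Protocol 6.1 describes the secondary endpoints as covering audibility |
| Visit 2 is the only postoperative bone conduction visit, whereas aided sound field is also taken at Months 3 and 6 (protocol section 2) | Protocol 3.2.2.2 uses PTA 4 for the unaided-to-aided audibility gain |
| | The endpoint runs from Baseline; bone conduction is scheduled at Screening |

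The frequencies do not settle it. The sound-field list is exactly 0.5, 1, 2 and 4 kHz, but bone conduction is also measured at all four (protocol 6.3.1.2).

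**4. Pass probability.** With d = true mean of delta divided by its SD, P(pass) = 1 − F(t_crit; df = n − 1, noncentrality d√n), where F is the noncentral t distribution function. For n = 50, t_crit = 2.0096; for n = 40, t_crit = 2.0227.

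| True d | n = 50 | n = 40 |
|---|---|---|
| −0.4 | 0.0001% | – |
| −0.2 | 0.04% | 0.07% |
| 0 | 2.5% | 2.5% |
| 0.1 | 10.3% | 9.0% |
| 0.2 | 28.3% | 23.4% |
| 0.4 | 79.2% | 69.4% |

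The n = 40 column shows what happens if bone conduction is numeric in only 40 children.

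*Bone conduction.* With true change zero, P(pass) equals alpha, 2.5%, whatever the SD, n or sign. A simulation of 400,000 trials gave 2.5% in each tail. With the sign corrected, 80% power needs a true improvement of 0.404 SD at n = 50 (0.454 SD at n = 40). At an assumed SD of 10 dB and n = 50 that is 4.0 dB. Run literally, the positive rows apply to worsening: a true loss of 0.4 SD would meet the objective 79.2% of the time.

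*Sound field.* As an illustration, take the 31.7 dB gain in protocol 3.2.2.2 (6 months, ages 10 to 17) and an assumed SD of 10 to 30 dB. As written, d runs from −31.7/10 = −3.17 to −31.7/30 = −1.06, and P(pass) is essentially 0. With the sign corrected it exceeds 99.9% throughout.

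**5. Endpoint 4.** SNR-50 is the ratio needed for 50% correct (protocol 6.3.2.2.2), so lower is better, yet protocol 8.3.2.4 and SAP 5.6.5.1 use 6 months minus preop with Ha: delta > 0. If SNR-50 improves by 0.2 or 0.4 SD, P(pass) as written is 0.04% or about 0.0001%.

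**6. Sequence.** If the order is the numbering and mean bone conduction is unchanged, formal testing stops at or before endpoint 2 at least 97.5% of the time.

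**The case against.** The strongest reply is that bone conduction is clearly the likelier reading. The objective naming it appears in the synopsis, protocol 5.2 and the SAP. Protocol 6.1.1 compares the audibility tests with the 3- and 6-month evaluations, not week 4. Screening and Baseline share the same Day −60 timing, and the formula says only preop. This stands, and it reduces the weight of the sound-field scenario. It does not remove the need to name the measure, and it makes the superiority problem more pressing.

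Second, the documents never say that unchanged bone conduction is the hoped-for result. The cited series reporting no alteration (protocol 3.2.2.1) covers 10 adults aged 30 to 78. That is fair: zero change in children aged 5 to 11 is an inference. The pass rate nevertheless remains low for small true gains.

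Third, the consequence is limited. The primary safety endpoint has no test, sample size is not driven by power, and every secondary endpoint is reported with a 95% interval (protocol 8.6.2). The stated intent also makes literal programming less likely. All true, but these are the study's only formal tests, and intent cannot settle which measure is meant.

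Fourth, the study is open-label, so Visit 2 data may already be visible to the sponsor, and choosing a measure or margin now may not count as fully prespecified. This is a real limit on the remedy and a reason to act early.

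**Conclusion.** The concern holds and must be fixed. The sign contradiction is present in both documents and needs no assumption to demonstrate. The measure is undefined in both, with bone conduction the likelier reading.

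Under bone conduction, the 2.5% pass rate at zero change is exact and free of any SD assumption; whether zero is the true change is inferred from one small adult series and the stated purpose of the test. Under sound field, the fault in the test is the sign alone, but objective 2 is then left without an endpoint. That illustration rests on an older cohort, a later time point and assumed SDs. The effect on CNC depends on the testing order being the endpoint numbering.

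**What to change.** Before the 6-month database lock (protocol 13.3), and as early as possible, amend protocol 8.2.2.2 and 8.3.2.2 and SAP 5.6.3:

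1. Name the measure, ear, listening condition and both visits.
2. Align the sign and hypothesis with that measure.
   - *Sound field:* delta = unaided Baseline PTA minus aided Visit 2 PTA with Osia 2, Ha: delta > 0. Report the bone conduction change from Screening to Visit 2 with its 95% interval, so that objective 2 is answered.
   - *Bone conduction:* delta = Visit 2 minus Screening, stating that positive means worse. Test H0: mean ≥ M against Ha: mean < M, met if the upper limit of the planned two-sided 95% interval is below a margin M that the sponsor justifies. Use the same null and direction in the Sign test of SAP 5.6.3.3. State how vibrotactile responses enter the PTA and whether they count as missing for the imputation in SAP 5.6.3.2. A simpler alternative is to report bone conduction descriptively, outside the testing sequence.
3. Correct endpoint 4 (protocol 8.3.2.4, SAP 5.6.5.1): delta = BKB preop minus BKB at 6 months, Ha: delta > 0.
4. State the testing order. Whether a no-harm endpoint should stand ahead of CNC and BKB-SIN is the sponsor's choice.

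The cost is wording, plus a justified margin if bone conduction is tested. Both measures are already scheduled. The price under bone conduction is that endpoint 2 would support a no-harm statement, not an improvement claim. Its power depends on a margin and SD that the documents do not give. With assumed values and true change zero, a 5 dB margin with SD 10 dB (5/10 = 0.5 SD) gives 93.4% with 50 evaluable children and 86.9% with 40. A 3 dB margin with SD 8 dB (3/8 = 0.375 SD) gives 73.9% and 63.8%. The case of 40 assumes that none of the minimum 10 children with single-sided deafness has a numeric value and that nothing is imputed.
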